5. TREATMENT PLAN AND STUDY SCHEMA

5.1 Study Design

This is a single-arm open-label phase Ib and phase II clinical study assessing the safety and relative efficacy of concurrent talimogene laherparepvec in combination with radiotherapy in patients with soft tissue sarcomas. Patients will be treated with neoadjuvant radiation and weekly intratumoral injections of talimogene laherparepvec. Weekly injections of talimogene laherparepvec will be continued until surgery. Surgery will be performed 4-6 weeks from the end of radiation therapy to allow for resolution of acute toxicities per current standard of care.

Phase 1b:

The phase Ib portion of this study is to ensure the safety and tolerability of talimogene laherparepvec in combination with EBRT as assessed by incidence of dose-limiting toxicities (DLT). Although this combination has been shown to be safe and well tolerated in several other tumor types including melanoma and head & neck cancers, this combination has not been studied in sarcoma patients. EBRT will be given at the standard dose for resectable soft tissue

sarcomas according to the NCCN sarcoma guidelines.² Patients will receive 50 Gy over 5 weeks, during which time they will be receiving weekly injections of talimogene laherparepvec. Weekly injections of talimogene laherparepvec will be continued until surgery 4-6 weeks later. Surgery will be performed 4-6 weeks from the end of radiation to allow for adequate tissue healing and resolution of acute toxicities.

[figure not shown]
Talimogene laherparepvec will be dosed at an initial dose of up to 4.0 mL of 10^6 PFU/mL on day 1 of week 1, followed by the target dose of up to 8.0 mL of 10^8 PFU/mL (Dose 0) three weeks later on day 1 of week 4, and dosed weekly until surgery. Initially 3 patients will be entered at the Dose 0 (following initial dose of up to 4.0 mL of 10^6 PFU/mL on day 1 of week 1) for talimogene laherparepvec and be monitored at this weekly dose through 4 injections, when safety issues will be addressed. Data from safety analysis will be reviewed with Amgen Medical and Safety team. If none or one of the 3 patients shows a DLT, three more patients will be entered into the study at this dose and be monitored at this weekly dose through 4 injections. If none or one of these 6 patients shows a DLT, this is the dose that will be used for the phase II relative efficacy assessment. Otherwise, talimogene laherparepvec dose will be deescalated and dose -1 will be explored as outlined below in Table 1. For this protocol DLT will be defined as an attributed adverse event (definite, probable or possible) that meets the criteria in Section 6.2.

Phase 2:

The phase 2 part of the study will provide an estimate of the relative treatment effect of talimogene laherparepvec in combination with preoperative EBRT in subjects with histologically confirmed diagnosis of locally advanced STS that is unresectable with clear wide margins, for which preoperative radiotherapy is considered appropriate, as measured by pathological response rates. Twenty- eight (28) patients will be enrolled into the phase 2 portion of this protocol.

As above, patients will receive the first dose of talimogene laherparepvec 4.0 mL of 10^6 PFU/mL on day 1 of week 1, and followed three weeks later by weekly injections at Dose 0. Weekly injections of talimogene laherparepvec will be continued until surgery. The EBRT will be given at the standard dose for resectable soft tissue sarcomas according to the NCCN sarcoma guidelines.² Patients will receive preoperative radiation at a dose of 50 Gy over 5 weeks starting around week 4, and continued concurrently with weekly injections of talimogene laherparepvec. Subjects should be followed by clinic visit every 12 weeks for approximately 24 months after the end of the treatment phase, at which time the initial survival data and disease recurrence will be assessed. Subjects will be followed for an additional 3 years for survival and disease recurrence after that according to the standard-of-care. Please see study calendar in Section 10.

Study Timeline Schema:

[figure not shown]

First dose of TVEC

[figure not shown]
Complete XRT

Complete TVEC → MRI of tumor → then Surgery

Phase 1b schema:

Phase 2 schema:

Talimogene Laherparepvec Dose Levels:

Dose 0 = talimogene laherparepvec up to 8.0 mL of 10⁸ PFU/mL dosed weekly

Dose -1 = talimogene laherparepvec up to 8.0 mL of 10⁸ PFU/mL dosed every 2 weeks.

- Initial dose for all = talimogene laherparepvec up to 4.0 mL of 10⁶ PFU/mL

Rationale for Talimogene Laherparepvec Dosing

Multiple studies have documented the efficacy and safety of talimogene laherparepvec in melanoma and head and neck cancer patients.²⁴⁻²⁶ In a phase I study to evaluate the safety, bio-distribution, and biological activity of differing dose levels of talimogene laherparepvec in patients with advanced solid tumors, Hu et al identified that subjects who are seronegative for HSV-1 more commonly developed febrile flu-like symptoms and erythematous skin rashes at higher initial doses of talimogene laherparepvec (10^7 and 10^8 PFU/mL) compared to a decreased initial dose of 10^6 PFU/mL.²⁷ Additionally, in a phase I/II upward-titration study to assess the safety and biological activity of three dose levels of talimogene laherparepvec (all initial doses were 10^6 PFU/mL, followed by subsequent doses of 10^6 , 10^7 or 10^8 PFU/mL) a greater mean decrease in tumor size was observed in patients receiving subsequent doses of 10^7 PFU/mL or higher compared to those administered only 10^6 PFU/mL for all doses. The study also reported that none of the injected tumors in the lowest dose cohort (10^6 PFU/mL) had resolved by the end of the treatment period, whereas 36.5% (12/32) of measurable tumors resolved (i.e., were no longer detectable) at the higher dose levels, suggesting that talimogene laherparepvec has a dose-related effect on tumor necrosis.²⁶ For this study all subjects will be treated with an initial dose of talimogene laherparepvec 10^6 PFU/mL, followed by 10^8 PFU/mL for all subsequent doses in accordance with the currently approved maximum tolerated dosing per the above phase I studies. A Phase 1b/2 trial in patients with advanced soft tissue sarcomas of the trunk and extremities was conducted at University of Iowa. As per the safety results presented there were no dose limiting toxicities noted at doses of 4 mL of 10^8 PFU/mL. One of the possibilities for failure to reach the primary endpoint was the lower amount of drug injected relative to the size of sarcomas. Hence a trial amendment with higher injectable dose of the drug is being proposed.

5.2 Study Agent Administration: Talimogene Laherparepvec

5.2.1 Talimogene Laherparepvec Dose Levels:

- Initial dose for all = talimogene laherparepvec up to 4.0 mL of 10^6 PFU/mL
- Dose 0 = talimogene laherparepvec up to 8.0 mL of 10^8 PFU/mL dosed weekly
- Dose -1 = talimogene laherparepvec up to 8.0 mL of 10^8 PFU/mL dosed every 2 weeks.

Dosing Schedule:

Patients will be treated with 50 Gy over 5 weeks and concurrent weekly injections of talimogene laherparepvec. Weekly injections of talimogene laherparepvec will be continued until surgery, about 4-6 weeks later.

Dosing Information:

Talimogene laherparepvec will be only administered by intratumoral injection into soft tissue tumors with or without image ultrasound guidance. Talimogene laherparepvec must not be administered into visceral organ metastases.

The initial dose of talimogene laherparepvec is up to 4.0 mL of 10^6 PFU/mL. Subsequent doses of talimogene laherparepvec are up to 8.0 mL of 10^8 PFU/mL. The maximum volume of talimogene laherparepvec administered at any dose is 8.0 mL for any individual lesion. The maximum dose in any one treatment is 8.0 mL. Investigators are encouraged to use the

maximum amount whenever lesions allow. In response to severe AEs, dose delays and dose de-escalations may be employed, but dose volume reduction for AEs is not allowed – see Section 6. However if in the course of administration of talimogene laherparepvec the subject cannot tolerate the full dose due to an injection-related AE such as pain, the total volume given should be recorded, and the reason for intolerance should be documented as an AE.

[figure not shown]
Treatment will be administered on an outpatient basis. Reported adverse events and potential risks are described in Section 7. Appropriate dose modifications are described in Section 6. No investigational or commercial agents or therapies other than those described below may be administered with the intent to treat the patient's malignancy.

5.2.2 Lesion site preparation

- Talimogene laherparepvec is only to be administered by intralesional injection into soft tissue tumors with or without image ultrasound guidance. Talimogene laherparepvec must not be administered into visceral organ metastases.
- The injection site may be pre-treated with a topical anesthetic agent or an injectable local anesthetic; however, a local anesthetic must not be injected directly into the lesion.
- Swab the lesion and surrounding areas with alcohol, allow to dry.

5.2.3 Lesion injection

- All personnel handling talimogene laherparepvec or material contaminated with talimogene laherparepvec must observe safety precautions (e.g., wear a laboratory coat, safety glasses and gloves).
- Inject talimogene laherparepvec intralesionally:
 - a) A single point of insertion is recommended; multiple insertion points may be used if the tumor is larger than the radial reach of the needle.
 - b) Talimogene laherparepvec should be injected along multiple different tracks within the lesion in order to obtain as wide dispersion as possible.
 - c) Distribute talimogene laherparepvec within the lesion through the insertion point using the radial reach of the needle in different directions to evenly distribute.

- Avoid premature extraction of needle.
- After dosing, the injection site should be swabbed with alcohol and pressure should be applied with gauze for several seconds after injection.
- The injection site should be covered with an absorbent pad and dry occlusive dressing.
- Dispose materials used during injection (e.g., gloves, needles, gauze) in accordance with local/regional and institutional requirements for biohazardous waste.

5.2.4 Radiation Therapy

External beam radiation therapy will be given at the standard dose for resectable soft tissue sarcomas according to the NCCN sarcoma guidelines.² Patients will receive 50 Gy over 5 weeks, during which time they will be receiving weekly injections of talimogene laherparepvec. Weekly injections of talimogene laherparepvec will be continued until surgery 4-6 weeks later. Surgery will be performed 4-6 weeks from the end of radiation to allow for adequate tissue healing and resolution of acute toxicities.

Radiation therapy for this protocol is as per currently used standard pre-operative radiation therapy at the University of Iowa even for non-protocol patients.

Selected guidelines from previously conducted Radiation Therapy Oncology Groups (RTOG) studies are briefly summarized for this protocol.

Preoperative Radiation therapy (3D-CRT or IMRT)

Either 3D conformal radiotherapy or intensity modulated radiation therapy may be utilized for adequate tumor coverage and to meet the dose constraints for critical normal structures.

Radiation treatment planning scans and immobilization:

CT scans with patient in a stable and comfortable position will be used for planning. MRI scans are optional and may be used for co-registration with CT for tumor localization as needed. VacLoc or other immobilization devices can be used for immobilization.

Target volumes and treatment field:

Gross Target Volume (GTV): Outline of the tumor as seen on CT or CT/MRI fusion.

Clinical Target Volume (CTV): CTV = GTV plus 4 cm margins in the proximal and distal directions. However the margin can be reduced if it extends beyond the compartment, the field can be shortened to include the end of a compartment. The radial margin from the lesion should be 1 cm. It can be reduced in areas confined by the fascial barrier or bone or skin surface.

Planning Target Volume (PTV): Include CTV and error of setup and organ motion. Typically PTV includes CTV plus 1 cm in all dimensions. Final PTV is usually GTV + 5 cm longitudinal and 2 cm radial, except where restricted by the compartment end, fascia, bone or skin surface. Use of bolus on the skin surfaces is optional as needed. Where applicable, biopsy scars should be bolused with appropriate thickness specific to the energy of the photon beam.

Dose Specifications:

A dose of 50 Gy in 25 daily fractions will be prescribed to the planning target volume (PTV) using linear accelerator and megavoltage photon beams with energies of 6MV or greater.

Prescribed dose should cover > 90% of the PTV. More than 95% of the PTV should receive > 95% of the prescribed dose. No more than 20% of the PTV will receive $\geq 110\%$ prescription dose.

Precautions and Dose Constraints for critical structures:

Radiation dose to normal tissues should be kept within the accepted normal tissue tolerances.

Every effort should be made to:

- a) Avoid treating the full circumference of an extremity;
- b) Avoid treating anus, urogenital tract, perineum and genitalia; if the tumor is close to these structures, typically less than 50% volume of the anus and vulva should receive 30 Gy; less than

50% volume of the testis should receive 3 Gy, if the patient prefers to reserve fertility;

- c) Avoid treating the lung, through use of appropriate shielding and treatment planning; less than 20% of the lungs should receive 20 Gy (V20);
- d) Avoid dose maximums in areas where surgical scars will be placed; this may require reviewing treatment plans with the surgeon;
- e) If possible, avoid treating skin over areas commonly traumatized to full dose (e.g., the elbow, knee, shin, femoral neck).
- f) If possible, less than 50% of any joints (including shoulder, elbow and knee) should receive 50 Gy.
- g) Less than 50% of kidney volumes should receive 18 Gy.
- h) No more than 50% of normal weight-bearing bone within the radiation field should receive 50 Gy except when the tumor invades the bone or when there is circumferential involvement of the tumor more than a quarter of the bone or when the bone will be resected in a subsequent surgical resection after radiation.

For any other normal tissue structures, no radiation dose more than the established TD5/5 limit should be given.

Image Guidance and Verification Devices

Portal films or conebeam CT images should be used for target localization and alignment. Daily conebeam CT will be preferred and dose from daily conebeam should be included in the final dosimetry.

Postoperative Radiotherapy Boost

External Beam or Brachytherapy boost can be given at the discretion of the radiation oncologist, to the positive tumor margin (residual tumor) only plus a margin of 1 cm within 2 weeks following surgery or after adequate wound healing has occurred.

The target volume for postoperative radiotherapy will be the residual tumor bed as defined by the surgical and pathological findings.

External Beam Radiotherapy

Postoperative external beam boost dose is 16 Gy in 8 fractions (once a day).

Brachytherapy

High-dose-rate (HDR) brachytherapy as a boost to the positive tumor margin can be used as an alternate to external beam radiotherapy. Brachytherapy catheters are placed at an interval of 0.5 -1.0 cm on the residual tumor bed (positive margin) plus a margin of 1 cm during surgery. Skin surface dose should be kept below 50% of the prescription dose unless positive margins occur in cutaneous or subcutaneous tissues. It is not necessary to include the entire surgical bed, drain sites and wound.

Brachytherapy should not start until day 5 after the surgery (day 0) and must be completed within 2 weeks following surgery.

For HDR brachytherapy, 4 fractions of 3.4 Gy are delivered b.i.d, with an interval of at least 6 hours between fractions.

Radiation Therapy Adverse Events

Acute: Wound complications of any grade are expected to develop in about one third of patients. Other common radiation adverse events include: fatigue, regional alopecia, diarrhea, skin erythema and desquamation within the treatment fields, and reduction in blood counts.

Long-term: Common long-term treatment adverse events include: lymphedema of the extremity receiving radiation and surgery, subcutaneous fibrosis, and joint stiffness. Much less common radiation adverse events include bowel injury, osteoradiation necrosis, and bony fracture in the radiation field. There also is a risk of secondary malignancy occurring in the irradiated field.

5.3 General Concomitant Medication and Supportive Care Guidelines

Patients should receive full supportive care, including transfusions of blood and blood products, antibiotics, antiemetics, etc., when appropriate. The reason(s) for treatment, dosage, and the dates of treatment should be recorded.

All other protocol-required therapies including, topical anesthetic or an injectable local anesthetic medications used for pretreatment of the talimogene injection site and oral or systemic treatments required for management of immune-mediated AEs that are to be obtained commercially.

Throughout the study, investigators may prescribe any concomitant medications or treatments deemed necessary to provide adequate supportive care. All prescription and nonprescription concomitant medication administered up to 28 days prior to enrollment, on an ongoing basis at enrollment, as well as changes in such concomitant medication, and any new concomitant medication taken while the subject is on study, should be recorded up to 30 days after the last dose of talimogene laherparepvec.

5.4 Duration of Therapy

Concurrent immunoradiotherapy with a total of 50 Gy of radiation and weekly talimogene laherparepvec intratumoral injections will be given over 5 weeks. Then, weekly intratumoral injections of talimogene laherparepvec will be continued until surgery is performed around 4-6 weeks later. In the absence of treatment delays due to adverse event(s), treatment may continue until surgical resection of the tumor, or until one of the following criteria applies:

- Intercurrent illness that prevents further administration of treatment,
- Unacceptable adverse event(s),
- Patient decides to withdraw from the study, or
- General or specific changes in the patient's condition render the patient unacceptable for further treatment in the judgment of the investigator.

5.5 Duration of Follow Up

Safety Follow up Visit

Upon permanent discontinuation from the study treatment for any reason, the following procedures will be performed approximately 30 (+7) days after the last dose of Talimogene Laherparepvec:

- Recording of concomitant medications and AE/SAE(s)
- Physical examination including weight, vital signs and ECOG performance status assessment
- Local laboratory tests including the following:
 - Hematology panel
 - Chemistry panel
 - Serum or urine pregnancy test for female subjects of childbearing potential

Long-term Follow up

Following the end of treatment, subjects will be followed according to standard of care (approximately every 12 -16 weeks +/- 2 weeks), as per NCCN guidelines and at the discretion of the treating physician, at which time disease recurrence and survival status will be assessed for up to 5 years. Data for disease recurrence and survival status only will be collected per chart review, phone call or email.

End of Study

The end of study for each subject is defined as the date the subject withdraws full consent from the study, completes the safety follow-up visit or the long-term survival follow-up whichever is later, or death.

5.6 Criteria for Removal from Study

Talimogene laherparepvec is to be permanently discontinued for subjects meeting any of the following criteria:

- The subject, for any reason, requires treatment with another anticancer therapeutic agent for treatment of the study disease (other than the exceptions noted in protocol, if applicable). In this case, discontinuation from the treatment occurs immediately upon introduction of the new agent.
- Clinical relevant disease progression as defined in the study protocol.
- Immune-mediated adverse events have been observed in subjects receiving talimogene laherparepvec. These have included pauci-immune glomerulonephritis, vasculitis, and pneumonitis; however, immune-mediated adverse events can potentially involve any organ system. Permanently discontinue talimogene laherparepvec if dosing is delayed by more than 4 weeks due to a Grade 2 or greater immune-mediated adverse event (with the exception of vitiligo), allergic reactions, or urticaria attributed to talimogene laherparepvec.
- Plasmacytoma has been observed with the administration of talimogene laherparepvec. Permanently discontinue talimogene laherparepvec if development of a plasmacytoma is observed.

- Any talimogene laherparepvec-related non-hematologic or hematologic toxicities Grade 3 or greater that, in the opinion of the investigator, would require a dose delay of greater than 4 weeks or discontinuation of therapy.
- A female subject becomes pregnant or fails to use 2 highly effective methods of contraception (for those subjects who are able to conceive).
- A female subject breast feeds while on study treatment.
- A male subject fails to use a highly effective method of contraception as described in Section 7.5.
- Intercurrent medical illness that, in the judgment of the investigator, would make continued treatment with talimogene laherparepvec dangerous for the subject.

6. DOSING DELAYS/DOSE MODIFICATIONS

6.1 Dose Delays

If talimogene laherparepvec treatment was delayed due to adverse events or other reasons by > 1 week, that dose will be deemed to have been missed and the subject will proceed to the next scheduled treatment visit.

If dose-limiting toxicities occur, talimogene laherparepvec administration should be delayed until the DLT has resolved to at least CTCAE version 4.0 Grade 1 (see Appendix E). Dosing of talimogene laherparepvec could also be delayed for active herpetic cutaneous or mucosal lesions, herpes labialis, or active dermatoses in the region of the injected tumors. Talimogene laherparepvec should be discontinued for subjects with evidence of systemic herpetic infection, herpetic keratitis, encephalitis, or evidence of other disseminated herpetic infection or any herpetic infection requiring treatment with acyclovir or a similar agent.

If talimogene laherparepvec dosing is delayed by more than 4 weeks due to the occurrence of DLT or adverse events that are related to talimogene laherparepvec, then treatment should be discontinued. If talimogene laherparepvec dosing is delayed by more than 4 weeks for reasons other than treatment-related toxicity, the case must be reviewed by the sponsor of the investigator sponsor study (ISS) to determine if the subject can resume talimogene laherparepvec therapy.

If the subject requires corticosteroid dosing of > 10 mg prednisone daily (or equivalent) and/or other immunosuppressive medication for related toxicities, talimogene laherparepvec dosing must be held until the corticosteroid dose has decreased to < 10 mg prednisone daily (or equivalent) and the administration of the other immunosuppressive medication has discontinued.

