6.2 Dose Limiting Toxicities

Definitions of dose-limiting toxicity:

Toxicity will be evaluated according to CTCAE version 4.0. DLT will be defined as any of the following talimogene laherparepvec-related toxicity or related to the combination of talimogene laherparepvec and radiation therapy during treatment and through week 8:

- Grade 3 or greater immune-mediated adverse events
- Grade 3 or greater allergic reactions.
- Any grade plasmacytoma
- Any other unexpected grade 3 or greater hematologic or non-hematologic toxicity, with the exceptions of:
 - Any grade of alopecia.
 - Expected radiation related skin toxicity of any grade.
 - Grade 3 arthralgia or myalgia.
 - Brief (< 1 week) grade 3 fatigue.
 - Grade 3 fever.
 - Grade 3 diarrhea or vomiting responding to supportive care.

Of note, unless an alternative etiology has been identified, signs and symptoms of any disease process described above as a DLT should be considered immune-mediated.

If unexpected DLT occurs, talimogene laherparepvec administration should be delayed until the DLT has resolved to at least CTCAE version 4.0 grade 1. If dosing is delayed by more than 4 weeks due to the occurrence of unexpected adverse event that is considered related to talimogene laherparepvec, then the subject should be taken off treatment.

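### Sections 6.1 to 6.3 conflict with Appendix D for life-threatening hypersensitivity: no explicit stopping rule carries the contraindication into the dosing rules

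*Combined protocol and SAP*

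**What the plan says.** - **Section 6.2** lists "Grade 3 or greater allergic reactions" among the DLTs when related to the drug or to its combination with radiation. The DLT period runs "during treatment and through week 8".
- **Section 6.1** gives the general response to a DLT: "If dose-limiting toxicities occur, talimogene laherparepvec administration should be delayed until the DLT has resolved to at least CTCAE version 4.0 Grade 1". Its stopping rule depends on time: "If talimogene laherparepvec dosing is delayed by more than 4 weeks due to the occurrence of DLT or adverse events that are related" to the drug, treatment ends. Section 6.2 closes with much the same pair of rules for unexpected events.
- **Section 6.3** moves a patient who misses two doses in a row because of a DLT to every-2-week dosing.
- **Section 5.6** says "Permanently discontinue talimogene laherparepvec if dosing is delayed by more than 4 weeks due to a Grade 2 or greater immune-mediated adverse event", and the same sentence extends to "allergic reactions, or urticaria attributed to talimogene laherparepvec". A separate bullet covers related "toxicities Grade 3 or greater that, in the opinion of the investigator, would require a dose delay of greater than 4 weeks or discontinuation". For one other DLT it is unconditional: "Permanently discontinue talimogene laherparepvec if development of a plasmacytoma is observed".
- **Appendix D** contraindicates the drug, with no time or grade condition, in anyone who has had life-threatening hypersensitivity to it or to an excipient. Sections 7.4 and 7.6 point to this appendix as risk information.

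**The concern.** A life-threatening allergic reaction to the study drug is a DLT, so staff would look to Section 6; Section 5.2.1 also sends them there for dose modifications. What they find is an instruction to wait for recovery to Grade 1 and then carry on, with a forced stop only if recovery takes long enough. The trigger is how long dosing is interrupted, not how dangerous the reaction was. A severe allergic reaction can be brief, so the rule can miss the case that Appendix D has in mind.

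At stake is the safety of an individual patient who might be re-exposed to a drug that the protocol elsewhere says must not be given. The trial's inferences are not at stake.

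**Working it through.** The plan states no figure on this point. The check sets the rules side by side and then counts what the schedule leaves.

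**Step 1: which rule forces a stop?** Take a life-threatening allergic reaction attributed to the drug that settles to Grade 1 within 4 weeks. I assume it is graded 3 or higher.

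| Place | Trigger | Stop mandatory in this case? |
|---|---|---|
| 5.4 | Adverse event considered unacceptable | No; a judgement |
| 5.6, immune-mediated and allergic bullet | Delay over 4 weeks | No |
| 5.6, Grade 3 or above bullet | Investigator's opinion | Only once the investigator so judges |
| 6.1, DLT or related event | Delay over 4 weeks | No |
| 6.1, herpetic infection | Listed herpetic events | Not applicable |
| 6.2, closing paragraph | Delay over 4 weeks | No |
| 6.3 | Two consecutive doses missed for a DLT | No; continues biweekly |
| Appendix D | Past life-threatening hypersensitivity | Yes, as a contraindication |

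Only the last row bars further dosing whatever the delay and whatever the investigator's view, and none of 5.4, 5.6 or 6.1 to 6.3 cites it. The only appendix that 6.1 cites is E.

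If the week-8 limit in 6.2 closes the DLT period, a reaction in weeks 9 to 12 is not a DLT, and the hold to Grade 1 drops away too. The 4-week condition still applies, because 6.1 covers related adverse events as well as DLTs.

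**Step 2: can the 4-week condition be missed in practice?** Inputs: injections at week 1 and weeks 4 to 12 (Section 10.1 calendar); visits within 3 days either side (footnote a); first dose up to 4.0 mL at 10^6 PFU/mL, then up to 8.0 mL at 10^8 PFU/mL (Section 5.2.1).

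- Scheduled injections: 1 + (12 − 4 + 1) = 10.
- Gap from first to second dose: (4 − 1) × 7 = 21 days. With the window at both visits, 21 − 6 = 15 to 21 + 6 = 27 days.
- Reaction at week 1, settled by week 4: no delay and no missed dose, so neither the 4-week stop nor 6.3 applies. Injections left: 10 − 1 = 9.
- Reaction at week 4, settled before week 5: 12 − 5 + 1 = 8 left.
- Reaction at week 4, weeks 5 and 6 missed: the wait from week 5 to week 7 is 2 weeks, under the 4-week limit. Section 6.3 then gives weeks 7, 9 and 11, so 3 left.

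**Step 3: size of the next dose after a first-dose reaction.** First-dose maximum: 4.0 × 10^6 = 4 × 10^6 PFU. Next-dose maximum: 8.0 × 10^8 = 8 × 10^8 PFU. The ratio is 200, with twice the volume. Section 5.2.1 does not allow volume to be cut for adverse events, and 6.3 does not allow a lower concentration, so a planned reduced rechallenge is not available.

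**The case against.** The strongest reply is that the protocol already bars re-dosing. Appendix D is part of it and is unconditional. Section 4.1.3 admits no one previously given the drug, so a reaction from treatment with it would be expected to arise on study, and the contraindication must have that case in view. This stands. A reader might infer from Section 6 that the protocol permits re-injection after a life-threatening reaction; read as a whole, it does not. What remains is that Section 6 gives an instruction for this DLT that contradicts the appendix, and gives no sign of doing so.

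Second, there are routes to stop. An investigator can call the event unacceptable under 5.4, or judge under 5.6 that discontinuation is needed, after which the stop is mandatory. Serious events go to the monitoring committee within 24 hours (Appendix E), and Phase 1b safety data are reviewed with the manufacturer's medical and safety team (5.1). So it would be too strong to say that a patient is protected only by the investigator's discretion or by someone opening Appendix D. But reporting and review are not stopping rules, and the protocol does write event-specific stops for plasmacytoma, pregnancy and systemic herpetic infection. This event is absent from that list.

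Third, Grade 4 and life-threatening are not interchangeable here. Section 7.2 describes Grade 4 as life-threatening or disabling, and offers that scale only where CTCAE has no specific grading. That is fair, and the remedy should use Appendix D's criterion rather than a grade number.

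Finally, a reader might infer from 6.1 that a plasmacytoma, also a DLT, may be held and re-injected. Section 5.6 requires a permanent stop and governs, so that is a missing cross-reference and nothing more.

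**Conclusion.** The point holds as a conflict between the dosing rules and Appendix D. For life-threatening hypersensitivity that settles without a delay of more than 4 weeks, 6.1 to 6.3 followed literally lead to further dosing, and 5.6 forces a stop only through the investigator's opinion. The contraindication exists but is not written as a stopping rule where staff would apply one.

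The schedule leaves between 3 and 9 of the 10 injections in the cases worked above. These counts show that the 4-week condition can fail to trigger; they do not forecast that anyone would be re-dosed. The documents give no rate for the event, it is rare, and no probability is claimed. The conclusion assumes that a life-threatening reaction is graded at least 3 and that an on-study reaction counts as history before the next injection. Grade 3 reactions that are not life-threatening are outside the point.

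It should be fixed, on patient-safety grounds. Endpoints, sample size, power and error rates are unaffected.

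**What to change.** 1. Add a bullet to Section 5.6: permanently stop at once for life-threatening hypersensitivity to talimogene laherparepvec or any of its excipients, regardless of the length of any delay, with a reference to Appendix D.
2. Add to the hold and biweekly rules in 6.1, 6.2 and 6.3: *except for events requiring permanent discontinuation under Section 5.6*. The same clause tidies the plasmacytoma cross-reference.

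The cost is one bullet and three short clauses at the next amendment. It adds no procedures, visits or patients.
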